4.2 PRIMARY ANALYSIS

There are two primary effectiveness endpoints. The primary effectiveness endpoints will not be used to support labeling claims.

A1C

The end of Phase 2 (~13 weeks) A1C will be compared to baseline A1C as measured by the core laboratory by calculating the change from baseline in A1C at Visit 13 (~13 weeks) for each subject.

The change in A1C is calculated as the A1C at Visit 13 minus baseline A1C. The null hypothesis associated with this endpoint states that the mean change in A1C is greater than or equal to zero. Rejection of the null hypothesis indicates that the observed data support the alternative hypothesis that the mean change in A1C is less than zero (indicating improved glycemic control). The hypotheses associated with the first primary effectiveness endpoint are defined as:

H0: µ ≥ 0 H1: µ < 0

where μ is the mean of the per subject differences in A1C from baseline to Visit 13.

Percentage of Time in Range 70-180 mg/dL

The percentage of time in range (TIR) 70-180 mg/dL during Phase 2 of hybrid closed-loop will be compared to Phase 1 by calculating the change between the time in range percentages between Phase 2 and Phase 1 for each subject. The change is calculated as the percentage of time in range during Phase 2 minus the percentages of time in range

Statistical Analysis Plan

during Phase 1. The null hypothesis associated with this endpoint states that the mean change in percentage of time in range 70-180 mg/dL is less than or equal to zero. Rejection of the null hypothesis indicates that the observed data support the alternative hypothesis that the mean change in percentage of time in range 70-180 mg/dL is greater than zero. The hypotheses associated with the second primary effectiveness endpoint are defined as:

H0: µ ≤ 0 H1: µ > 0

where μ is the mean of the per subject differences in percentage of time in range 70-180 mg/dL during Phase 2 (hybrid closed-loop) compared to Phase 1 (standard therapy).

Both primary effectiveness endpoints will be tested independently of each other for statistical significance using a paired t-test at a one-sided significance level of 1.25%.

The modified Intention to Treat (mITT) analysis set will be the primary analysis set used to analyze the primary effectiveness endpoints. The results based on the Per Protocol (PP) analysis set will be considered supportive.

4.3 SUBGROUP AND STRATIFIED ANALYSES

For the primary effectiveness endpoints, all data will be included in the primary analysis. Subgroup or stratified analyses may be presented. These may include but are not limited to:

- Day and night (daytime: 6AM to <12AM; nighttime as 12AM to <6AM)
- Length of time in HCL (e.g., Month 1, Month 2)
- Demographic measures (e.g., gender, race)
- Previous pump or CGM use
- BMI (≤25 vs >25 kg/m²)

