6.3.1 Secondary Endpoints

The secondary objective will be evaluated using the following per subject endpoints *with* prespecified hypotheses:

- Glucose metrics from system CGM during the hybrid closed-loop phase for Phase 2 will be compared to Phase 1 overall:
 - % of time > 180 mg/dL
 - % of time < 70 mg/dL

Additional per subject secondary endpoints *without* prespecified hypotheses used to evaluate the secondary objective include:

- A1C:
 - A1C at the end of Phase 2 (Visit 13), at 6 months (Visit 16), and at the end of Phase 3 (Visit 23; approximately 15 months)

- Change from baseline in A1C at the end of Phase 2 (Visit 13), at 6 months (Visit 16), and at the end of Phase 3 (Visit 23; approximately 15 months)
- Proportion of subjects demonstrating an improvement from baseline in A1C at the end of Phase 2 (Visit 13), at 6 months (Visit 16), and at the end of Phase 3 (Visit 23; approximately 15 months)
- Glucose metrics from system CGM during the hybrid closed-loop phase during Phase 2, and separately during Phase 3 will be compared to Phase 1 during the day, overnight, and overall:
 - Mean glucose
 - % of time in range 70-180 mg/dL
 - % of time in range 70-140 mg/dL
 - % of time > 180 mg/dL
 - % of time \geq 250 mg/dL
 - % of time \geq 300 mg/dL
 - % of time < 70 mg/dL
 - % of time < 54 mg/dL
 - Standard deviation
 - Coefficient of variation
- Percentage of time in hybrid closed-loop as proportion of overall device usage time during Phase 2, and separately during Phase 3
- Glucose management indicator (GMI) based on overall mean glucose during Phase 2 and, separately during Phase 3 will be compared to Phase 1
- Insulin requirements during Phase 2 and, separately during Phase 3 will be compared to Phase 1:
 - Total daily insulin (TDI) (units, units/kg)
 - Total daily basal insulin (units, units/kg)
 - Total daily bolus insulin (units, units/kg)
- Change from baseline in BMI (kg/m²) at end of Phase 2, and at the end of Phase 3

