7 SCREENING AND ELIGIBILITY

Potential subjects for this study will include individuals who have been diagnosed with type 1 diabetes are appropriate for pump therapy per investigator's assessment. Potential subjects will be selected at each clinical study site and screened accordingly. Clinical study sites will be advised to:

- Recruit subjects using insulin aspart, lispro, and glulisine also known as Humalog, Novolog, Admelog, or Apidra

Every effort will be made to establish eligibility of the patient prior to enrollment. Only patients who appear to meet all eligibility criteria will be enrolled in the study. Subject eligibility will be confirmed by study staff during a screening visit at the clinical site.

Blood draws will be collected as required to demonstrate study eligibility as noted below. Laboratory results within the last 6 months of the screening visit, with the exception of A1C, may also be used if available.

7.1 Visit 1

Visit 1 will be conducted in person at the clinical study site. This visit will assess eligibility and will include:

- Signing of informed consent/assent
- Review of inclusion/exclusion criteria
- Screening assessments performed following Table 1: Schedule of Assessments for Phase 1 and Phase 2

Informed Consent

Subjects who appear to meet the eligibility criteria will be required to have their parent/caregiver sign an Informed Consent Form (ICF) approved by the respective Institutional Review Board (IRB) before participating in the study. Failure to provide informed consent will render the subject ineligible for the study.

Subjects must also have a HIPAA (Health Insurance Portability and Accountability Act) release of protected health information (PHI) signed by their parent/caregiver. The release may be a stand-alone document or part of the informed consent.

After informed consent is obtained, a subject identification number will be issued to uniquely identify each subject. The unique identifier will be used to identify the subject throughout the study and will be used for all source documents and electronic Case Report Forms (eCRFs).

Inclusion Criteria

Subjects must meet all of the following criteria in order to be enrolled in the study:

1. Age at time of consent 2.0-5.9 years
2. Living with parent/legal guardian
3. Diagnosed with type 1 diabetes. Diagnosis is based on investigator's clinical judgment

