2.3 STUDY SCHEDULE

The study will consist of a 14-day outpatient standard therapy (ST) outpatient phase (Phase 1), a 13-week outpatient hybrid closed-loop (HCL) phase (Phase 2), and a 6-month hybrid closed-loop extension phase (Phase 3). The sponsor intends to submit results from Phase 2 for marketing clearance after data collection for Phase 2 is complete.

The Horizon[™] System has two modes. In Manual Mode, the system will function equivalently to the Omnipod DASH System. This includes delivering insulin at programmed basal rates and bolus amounts with the option to set temporary basal profiles. In Automated Mode, the system will support the use of multiple target glucose values. The

Statistical Analysis Plan

programmed basal rates, glucose targets and bolus calculator settings will inform the MPC (model predictive control) algorithm for insulin dosing parameters.

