2.5 RANDOMIZATION

This is a single-arm, multicenter, prospective clinical study where all eligible subjects will use the investigation device. Subjects will not be randomized.

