3.3 SECONDARY OBJECTIVE AND ENDPOINTS

The secondary objective is to evaluate additional glycemic measures of effectiveness of the Omnipod Horizon[™] Automated Glucose Control System. The secondary objective will be evaluated based on the following per subject endpoints *with* prespecified hypotheses:

- Glucose metrics from system CGM during the hybrid closed-loop phase for Phase 2 will be compared to Phase 1 overall:
 - Percentage of time in range > 180 mg/dL
 - Percentage of time in range < 70 mg/dL

Additional per subject endpoints *without* prespecified hypotheses used to evaluate the secondary objective include:

- A1C:
 - A1C at the end of Phase 2 (Visit 13), 6 months (Visit 16) and the end of Phase 3 (Visit 19)
 - Change from baseline in A1C at the end of Phase 2 (Visit 13), 6 months (Visit 16) and the end of Phase 3 (Visit 19)
 - Proportion of subjects demonstrating an improvement from baseline in A1C at the end of Phase 2 (Visit 13), 6 months (Visit 16) and the end of Phase 3 (Visit 19)
- Glucose metrics from system CGM during the hybrid closed-loop phase for Phase 2 and Phase 3 will be compared to Phase 1 during the day, overnight, and overall:
 - Mean glucose
 - Percentage of time in range 70-180 mg/dL
 - Percentage of time in range 70-140 mg/dL
 - Percentage of time in range > 180 mg/dL
 - Percentage of time in range ≥ 250 mg/dL
 - Percentage of time in range \geq 300 mg/dL
 - Percentage of time in range < 70 mg/dL
 - Percentage of time in range < 54 mg/dL
 - Standard deviation
 - Coefficient of variation
- Percentage of time in hybrid closed-loop as proportion of overall device usage time during Phase 2 and Phase 3
- Glucose management indicator (GMI) based on overall mean glucose during Phase 2 and Phase 3 will be compared to Phase 1
- Insulin requirements during Phase 2 and Phase 3 will be compared to Phase 1:
 - Total daily insulin (TDI) (units, units/kg)
 - Total daily basal insulin (units, units/kg)
 - Total daily bolus insulin (units, units/kg)
- Change from baseline in BMI (kg/m²) at end of Phase 2 and Phase 3

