To gather adequate safety and effectiveness data on the performance of the Omnipod Horizon[™] System, the study plans to enroll up to 80 subjects to obtain a minimum of 60 evaluable subjects. Subjects will be enrolled across 6-12 clinical study sites. No single site should enroll more than 24 subjects.

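### The optional BMI split at 25 kg/m² would leave one group nearly empty at ages 2.0-5.9, and the raw kg/m² BMI endpoint mixes growth with any change on the device

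*SAP*

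**What the plan says.** **Subgroup.** SAP 4.3 lists "BMI (≤25 vs >25 kg/m²" among possible subgroup analyses of the two primary effectiveness endpoints. The list is open-ended and optional: "Subgroup or stratified analyses may be presented". One cut serves all ages and both sexes.

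**Endpoint.** SAP 3.3 includes, among the secondary endpoints without a prespecified hypothesis, "Change from baseline in BMI (kg/m²) at end of Phase 2 and Phase 3". Protocol 6.3.1 and 13.1.4 define the same endpoint. Protocol 6.4 and SAP 7.6 add an exploratory BMI change at the last follow-up visit.

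**Population and design.** Eligibility (Protocol 7.1) requires "Age at time of consent 2.0-5.9 years". On numbers, SAP 4.1 states that "the study plans to enroll up to 80 subjects to obtain a minimum of 60 evaluable subjects". There is one arm, and SAP 2.5 confirms that "Subjects will not be randomized". Neither document mentions a BMI percentile, a BMI z-score or any adjustment of BMI for age or sex.

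**Timing.** SAP 2.3 describes "a 13-week outpatient hybrid closed-loop (HCL) phase (Phase 2", followed by a 6-month extension, and SAP 6.6 takes Visit 19 as the end of Phase 3. The protocol instead places that point "at the end of Phase 3 (Visit 23; approximately 15 months".

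**The concern.** A subgroup split is useful only if both groups hold enough subjects to describe. A BMI above 25 kg/m² takes a weight that few children of this height range are likely to reach, so the upper group would hold almost nobody and the lower group would simply repeat the overall result.

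The change endpoint has a different problem. BMI is weight divided by height squared, and both terms move in a growing child. A raw change from baseline therefore contains whatever BMI would have done with age over the same period, plus any change that goes with using the device. A control arm or a standardised score could take out the first part. The plan has neither. A reader of the results could take a growth-related shift for an effect of the system, or miss a real shift that growth offsets.

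**Working it through.** The documents state no BMI distribution, subgroup size or SD of BMI change, so there is no figure of the plan's own to reproduce. What follows uses the plan's inputs with labelled assumptions.

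**1. Weight needed to exceed the cut.** Weight = 25 × height². Heights are assumed as a range for this age.

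| Height (m) | Weight at BMI 25 (kg) |
|---|---|
| 0.85 | 18.1 |
| 0.95 | 22.6 |
| 1.00 | 25.0 |
| 1.05 | 27.6 |
| 1.15 | 33.1 |

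**2. Expected size of the upper group.** Expected count = N × p, and the chance that the group is empty = (1 − p)^N. N is 60 or 80 (SAP 4.1). The share p above the cut is assumed.

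| Assumed p | Expected, N=60 | Expected, N=80 | Chance empty, N=60 / 80 | Chance of 10 or more, N=60 / 80 |
|---|---|---|---|---|
| 1% | 0.6 | 0.8 | 55% / 45% | 0% / 0% (rounded) |
| 2% | 1.2 | 1.6 | 30% / 20% | 0% / 0% (rounded) |
| 5% | 3 | 4 | 4.6% / 1.7% | 0.07% / 0.65% |
| 10% | 6 | 8 | 0.2% / 0% (rounded) | 7% / 28% |

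As a cross-check, assume instead a normal BMI distribution with mean 16 to 17.5 and SD 1.5 to 3. The most generous pair (17.5 and 3) puts 0.62% above 25, or 0.37 of 60 and 0.50 of 80.

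**3. What 3 or 4 children can show.** The half-width of a 95% interval is t × SD/√n. Take the plan's own SDs of change (SAP 4.1): 10 percentage points for time in range and 0.8 for A1C.

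- n = 3: 4.303/√3 = 2.48, so ±24.8 points and ±1.99.
- n = 4: 3.182/√4 = 1.59, so ±15.9 points and ±1.27.

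The plan's assumed mean changes are 10 points and 0.5, so these intervals say nothing useful. With 0 or 1 child, no SD exists.

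**4. How growth alone could show in the change endpoint.** SAP 6.6 sets two-sided 5%, unadjusted, for any comparison of these endpoints. Suppose the device has no effect, 60 children have both measurements, and growth shifts mean BMI by d. A paired t-test then has noncentrality d√60/SD. For example, 0.2 × 7.746/0.8 = 1.94, which gives 48% rejection. The drift d and the SD of change are both assumed.

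| Assumed drift (kg/m²), either direction | Chance of a significant result, SD 1.0 to 0.6 |
|---|---|
| 0.1 | 12% to 25% |
| 0.2 | 33% to 72% |
| 0.3 | 63% to 97% |

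These are illustrations of sensitivity. The documents do not supply d.

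**5. When BMI can be calculated.**

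- *Baseline:* height and weight are taken at screening, where age and gender are also recorded (Protocol 7.1).
- *End of Phase 2:* at Visit 13 (Day 94), Protocol 9.9 takes height and weight only if the visit is in person, so some values can be missing.
- *End of Phase 3 in the SAP:* Visit 19 is Day 270, and 270/30.4 is about 9 months. Protocol Table 3 schedules no height or weight there for a child who continues.
- *End of Phase 3 in the protocol:* Visit 23 is Day 450, and 450/30.4 is about 15 months. Height and weight are scheduled at Visit 23 or study exit, and at early withdrawal.

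**The case against.** The strongest reply is that little depends on either item, and much of it stands.

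- **The subgroup is optional and the list is open.** A better split could be used without changing the SAP, and an empty group would do no harm to the primary analysis, which uses all data. That is right. A reader might infer that the trial will report an empty subgroup; the text supports only that the group would be nearly empty if the split were run. It remains the one body-size split that the SAP names.
- **BMI change is not a safety endpoint.** A reader might infer that it is there to detect undue weight gain and fails at that task. The documents do not support this. The named primary safety endpoints are the rates of severe hypoglycemia and DKA, and BMI change sits under the secondary effectiveness objective, without a hypothesis. SAP 6.6 says that results for these endpoints will not support clinical claims.
- **The growth effect has no size.** This also stands. The rejection rates above rest on assumed drifts and SDs, and on a test being run for BMI change. They should not be read as this trial's error rate. What does follow from the documents is that the raw change cannot be separated into growth and the rest.
- **A z-score can be derived later.** True, wherever age, sex, height and weight exist. Naming it before the analysis avoids a choice made after seeing the data.
- **A z-score does not create a control arm.** Correct. It removes average growth relative to a reference and leaves the remaining change unattributed.

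**Conclusion.** The point holds as a minor one. If presented, the split at 25 kg/m² would put about 0.6 to 4 of 60 to 80 children in the upper group, assuming that 1% to 5% exceed it. Even at an implausibly high 10% it would hold 6 to 8. It cannot inform on effect by body size. This rests on assumed shares, because the documents give no BMI data, but it holds across the plausible range.

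The BMI change endpoint, in raw kg/m² with a single arm and no standardisation, mixes expected age-related change with any change on the device. Size and direction are unknown from the documents. The mixing should be smaller at 13 weeks than at the end of Phase 3. A reader might take 15 months as the SAP's horizon, but that is the protocol's Visit 23. The SAP, which says that it prevails, stops at Visit 19, where the protocol schedules no height or weight for continuing children.

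Nothing here touches the primary endpoints, the safety endpoints or the two secondary endpoints under multiplicity control.

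**What to change.** 1. In SAP 4.3, replace the 25 kg/m² cut with a split on age- and sex-standardised BMI: either a percentile, or the trial median of the z-score, which gives two groups of about equal size.
2. In SAP 3.3, report change in BMI z-score beside raw change in kg/m² kept as description, wherever height and weight were measured. Name the growth reference, and give the number of children with both measurements at each time point.
3. State in the SAP that the z-score removes average growth relative to the reference and does not by itself attribute the remaining change to the device.
4. Reconcile the SAP's end of Phase 3 (Visit 19) with the protocol's (Visit 23) and with the height and weight schedule in Protocol Table 3.

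The first three items cost SAP wording and one derived variable from data already collected. The fourth costs SAP wording if the SAP moves to the protocol's visit. If Visit 19 stays, the protocol schedule would have to provide height and weight there, which means an amendment. No change to sample size or primary analysis is needed.

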5 ANALYSIS OF SAFETY

All adverse events reported during the study will be reviewed and adequately reported to comply with applicable regulations. All reportable AEs will be assessed by the investigator who will determine whether the event is related to the study procedures or related to the study device and whether the event meets any of the criteria for seriousness. The event will be considered serious if the event meets at least one criterion for seriousness.

5.1 MEDICAL MONITOR

An independent Medical Monitor will be responsible for individual and timely review of adverse events. The Medical Monitor will also adjudicate all serious adverse events (SAEs), including events of severe hypoglycemia and diabetic ketoacidosis (as well as all

events reported by the investigator as being device-related) for seriousness, severity, relationship to study device and procedure, whether the event is anticipated or unanticipated, and event categorization. The adjudication decision by the Medical Monitor will be used for the final classification of adverse events for regulatory reports, product labeling, and publications or presentation.

5.2 RELATIONSHIP TO STUDY DEVICE AND PROCEDURE

The causal relationship to the study procedures and the investigational device for each adverse event will be rated as follows:

- Unrelated: The event is not related to the procedures or the investigational device.
- Possibly Related: The temporal sequence is such that the relationship is not unlikely or there is no contradicting evidence that can reasonably explain the subject's condition. There is a possibility of any relation between the event and the procedures or the investigational device.
- Related: The temporal sequence is relevant or the event abates upon completion of the procedure/ investigational device, or the event cannot be reasonably explained by the subject's condition or comorbidities. The event is related or most likely associated with the procedures or the investigational device.

For the purposes of dichotomizing the causal relationship in safety summaries, events that are "Related" or "Possibly Related" will be considered related.

5.3 SEVERITY

The severity of the adverse event will be rated based upon the following grades:

- Mild: Usually transient, requires no special treatment, and does not interfere with the participant's daily activities
- Moderate: Usually causes a low level of inconvenience, discomfort or concern to the participant and may interfere with daily activities, but is usually ameliorated by simple therapeutic measures and participant is able to continue in study
- Severe: Interrupts a participant's usual daily activities, causes severe discomfort, may cause discontinuation of study device, and generally requires systemic drug therapy or other treatment

5.4 ANALYSIS OF ADVERSE EVENTS

Safety summaries and analyses will be based on all subjects that are enrolled in the study (i.e., Intention to Treat analysis set). All adverse events reported over the course of the study will be summarized and tabulated by study phase, event category, seriousness, severity, and relationship to the study procedures and the investigational device. Except where indicated, a subject reporting the same adverse event more than once will be

counted once when calculating the number and percentage of subjects with that particular event.

Adverse events leading to death or to discontinuation from the study will be listed separately. A listing of all adverse events will be provided. The primary safety endpoints will be presented by existing Dexcom G6 use at the time of screening (users and non-users). No formal tests of hypotheses are proposed for the safety endpoints.

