5.2 Study Design

This is a single-arm, multi-center, prospective clinical study. A total of up to 80 children aged 2.0-5.9 years with type 1 diabetes will be enrolled in the study in order to obtain a minimum of 60 evaluable subjects. Subjects will be considered evaluable if they have at least 8-weeks of data during Phase 2.

Subjects will be enrolled across 6-12 clinical study sites. The study schedule consists of the following three phases:

- 1) 14-day outpatient standard therapy phase (Phase 1)
- 2) 13-week outpatient hybrid closed-loop phase (Phase 2)
- 3) Hybrid closed-loop extension phase until the Omnipod 5 System is commercially available (Phase 3)

Figure 3: Study Schedule Timeline

Following subject screening, consenting, system training and enrollment, subjects will commence the standard therapy phase of the study.

Current Dexcom G6 CGM users may provide data from a 14-day period within the last 30-days. The CGM data meeting the minimum criteria must be the most recent data from the last 30-days. For non-G6 users, subjects will wear a study CGM, in blinded mode, to record glucose measurements over 14-days while subjects manage their diabetes at home per their usual routine while wearing a study CGM while remaining on their current MDI or pump therapy, and sensor, if applicable, for 14-days.

After completion of Phase 1 (the standard therapy phase), subjects and/or parents/guardians/caregivers will be trained on the system and transition to Phase 2 (the hybrid closed-loop phase) initiating treatment with the Omnipod Horizon™ System. A subset of subjects (N=40) will participate in activity for a minimum of 3 hours and dietary challenges over the course of 2 consecutive days during Phase 2. Phase 2 will be followed by the extension phase (Phase 3).

Table 1 and Table 3 outline the schedule of assessments for each phase of the study.

Table 1: Schedule of Assessments for Phase 1 and Phase 2

Assessment Schedule	Screening	ST1	ST2	Hybrid Closed-Loop (HCL)											EW ^a
				Phase 1			Phase 2								
Visit Number	1 ^b	2	3	4	5	6	7	8	9	10	11	12	13	UV ^c	
Study Day/Visit Window ^d	-30 to -14d HCL start	-14d to HCL start	-1d to HCL start	1	2 ±1d	3 ±1d	10 ±3d	24 ±3d	38 ±3d	52 ±3d	66 ±3d	80 ±3d	94 ±3d	N/A	
Telephone (T) or Office (O) Visit	O	O	O	O	T/O ^e	T/O ^e	T/O ^e	T/O ^e	T/O ^e	T/O ^e	T/O ^e	T/O ^e	T/O ^e	T/O ^e	O
Laboratory Assessments															
A1C	X (POC & Blood Draw)													X (Blood Draw)	X (Bloo d Draw)

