12 SAFETY

12.1 Types of Known Risks and Benefits

There are known risks and benefits. Most of the risks are not unique to the study and are typical for patients using insulin pumps, CGM, and BG meters.

The known risks are as follows:

- Hypoglycemia and/or hyperglycemia as a result of change in diet, activity, diabetes management or insulin regimen during the study.
- Hypoglycemia and/or hyperglycemia as a result of over or under delivery of insulin due to a device defect, failure or malfunction of any of the system components.
- Hypoglycemia, hyperglycemia, diabetic ketoacidosis, seizure, coma or death related to insulin administration, pump use or misuse, or Horizon™ System use or misuse.

- Use of the Pod (Omnipod® tubeless, insulin delivery pump) - Because the Pod uses only rapid-acting insulin, users are at increased risk for developing hyperglycemia if insulin delivery is interrupted. If it is untreated, prolonged hyperglycemia can quickly lead to diabetic ketoacidosis (DKA). DKA can cause symptoms such as breathing difficulties, shock, coma, or death. Further, occlusions can interrupt insulin delivery and lead to hyperglycemia or DKA. Other potential risks associated with using the Pod are:
 - Anaphylaxis (allergic shock)
 - Bruising at the Pod site
 - Bleeding at the Pod site
 - Erythema (redness at the Pod site)
 - Excoriation (raw skin at Pod site)
 - Pruritus (itching)
 - Induration (hardening of the skin at the Pod site)
 - Infection (can include heat, redness, swelling, pain, and drainage)
 - Inflammation (redness, swelling)
 - Skin reaction to adhesive at the Pod site
 - Papule (small, solid raised area on the skin similar to a pimple)
 - Pain or discomfort
 - Ulceration (skin sores)
 - Vesicles (blisters)
- Use of the CGM - risk of bruising, infection, pain and/or bleeding at the site of insertion, and skin site reaction to adhesive
- On rare occasions, the CGM sensor may break and leave a small portion of the sensor under the skin that may cause redness, swelling, or pain at the insertion site, and may require surgical removal.
- Blood sampling with fingerstick - minor discomfort and risk of infection at site of fingerstick

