13.6 Safety Analyses

13.6.1 Evaluation of Adverse Events

All adverse events reported over the course of the study will be summarized and tabulated by study phase, event category, seriousness, severity, and relationship to the study procedure and the investigational device. For the purposes of summarization, an event will be considered “Related” if the relationship was deemed as “Possibly Related” or “Related”. In cases where the same event is reported more than once per subject, the event will only be counted once in the incidence table(s).

Adverse events leading to death or to discontinuation from the study will be listed separately. A listing of all adverse events will be provided.

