3 STUDY OBJECTIVES AND ENDPOINTS

3.1 SAFETY OBJECTIVE AND ENDPOINTS

The safety objective is to evaluate the safety of the Omnipod Horizon[™] Automated Glucose Control System in preschool patients with type 1 diabetes. The safety objective will be evaluated by summarizing the following events during Phase 2:

- Incidence rate of severe hypoglycemia (events per person months)
- Incidence rate of diabetic ketoacidosis (DKA) (events per person months)

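### Adverse events other than severe hypoglycemia and DKA are planned only as once-per-child counts by phase, although phase lengths differ widely; event counts and person-month rates should be added

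*SAP*

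**What the plan says.** SAP 5.4 (Analysis of Adverse Events) states that all adverse events "will be summarized and tabulated by study phase, event category, seriousness, severity" and relationship to procedure and device. A child who reports the same event more than once is, except where indicated, "counted once when calculating the number and percentage of subjects with that particular event". On the denominator, the section says: "Safety summaries and analyses will be based on all subjects that are enrolled in the study". SAP 5.5 handles device deficiencies in a similar manner. A listing of all adverse events is planned, and no formal test is proposed for the safety endpoints.

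Protocol 13.6.1 is worded more firmly: for a repeat of the same event in one child, "the event will only be counted once in the incidence table(s".

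Two events are treated differently. SAP 3.1 defines "Incidence rate of severe hypoglycemia (events per person months", and likewise for DKA, for Phase 2. Protocol 6.1.1 asks for the same two rates in Phase 2 and separately in Phase 3. Neither document specifies an event count or a person-time denominator for any other adverse event.

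**The concern.** The two events with a rate are unlikely to recur on the device, because Protocol 12.7.1 discontinues device use after one episode of either. The events that can recur have no rate. One is prolonged hyperglycemia with ketosis (Protocol 12.3.4), which Protocol 12.2 allows to be attributed to a suspected occlusion or a dislodged cannula. Another is a sensor- or Pod-site reaction that is severe or treated (Protocol 12.3.2). Protocol 12.1 names occlusion as a route to serious harm: "Further, occlusions can interrupt insulin delivery and lead to hyperglycemia or DKA". Repeats are plausible: with a Pod change at least every 72 hours, a child uses at least about 94/3 = 31 Pods in Phase 2 and 356/3 = 119 in Phase 3 to Visit 23.

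Two things are at stake. First, the percentage of children with at least one event rises with time observed even when the risk is constant, so a table by phase cannot be read across phases of unequal length. Second, a child with five ketotic episodes in a phase adds no more to the table than a child with one, so the table does not show the burden of recurrent insulin interruption.

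**Working it through.** The plan states no figure on this point, so there is nothing to reproduce. The check derives the exposure and then illustrates its effect.

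**Exposure, from the documents**
- Phase 1: described in Protocol 5.2 as "14-day outpatient standard therapy phase (Phase 1". G6 users exempt from wearing the study CGM may go straight to Visit 4 (Protocol section 8), so their exposure can be about 0 days. If the CGM criteria are not met, the phase may be extended to 30 days (Protocol 8.2).
- Phase 2: Visit 13 is on Study Day 94 (Protocol 9.9), so about 94 days.
- Phase 3: Visit 19, which the SAP treats as the end of the phase, is on Day 270, and 270 − 94 = 176 days. Visit 23 is on Day 450, and 450 − 94 = 356 days. The protocol continues the phase until commercial availability, so it may be longer.

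**Assumptions**
- The documents give no event rate. I assume a constant rate of 0.02, 0.05 or 0.10 events per person-month, with Poisson events, full follow-up and one month = 30.4375 days.

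**Formulas**, with μ = rate × days / 30.4375
- Children with at least one event: 1 − exp(−μ)
- Share of events left out by once-only counting: 1 − (1 − exp(−μ))/μ

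Example at 0.10 over 94 days: μ = 0.10 × 94/30.4375 = 0.309. Children with an event: 1 − exp(−0.309) = 26.6%. Share left out: 1 − 0.266/0.309 = 14.0%. In 80 children, 24.7 expected events appear as 21.3 children.

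**Children with at least one event, same rate in every phase**

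| Rate per month | 14 days | 94 days | 176 days | 356 days |
|---|---|---|---|---|
| 0.02 | 0.9% | 6.0% | 10.9% | 20.9% |
| 0.05 | 2.3% | 14.3% | 25.1% | 44.3% |
| 0.10 | 4.5% | 26.6% | 43.9% | 69.0% |

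From unrounded values, the Phase 2 percentage is 5.9 to 6.5 times that of a 14-day Phase 1, with no change in risk. Phase 3 is 1.6 to 1.8 times Phase 2 at 176 days, and 2.6 to 3.5 times at 356 days.

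**Share of events left out of the table**

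| Rate per month | 94 days | 176 days | 356 days |
|---|---|---|---|
| 0.02 | 3.0% | 5.6% | 10.8% |
| 0.05 | 7.3% | 13.2% | 24.3% |
| 0.10 | 14.0% | 24.1% | 41.0% |

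At 0.01 per month the share is 1.5% at 94 days and 5.6% at 356 days, so for rare events the collapse is trivial. Clustering within children raises it: if individual rates follow a gamma distribution with shape 1 (an assumption) around a mean of 0.10, the shares become 23.6% and 53.9%.

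**Two further points on the denominator**
- An all-enrolled denominator in a later phase includes children who never entered it. That lowers the later percentage, opposite to the effect of longer exposure, so a reader cannot correct the table by eye.
- Phase 1 is sparse. With 80 children at a full 14 days it gives 80 × 14/30.4375 = 36.8 person-months, or about 1.8 expected events at 0.05 per month. Exempt G6 users reduce this further.

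**The case against.** The strongest reply is that the SAP sentence is not a mistake. A number of subjects can only be counted once per subject, the rule opens with an exception clause, and it does not bar event counts. The protocol wording is stricter, but the SAP prevails where they differ. This stands, but it leaves the gap: neither document specifies an event count or rate for these events.

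Several stronger readings are tempting, and the documents do not support them:
- *That all adverse events are collapsed.* They are not. Severe hypoglycemia and DKA, on which study success rests (SAP 2.4), are analysed per person-month.
- *That repeats are lost.* Every event is listed, the Medical Monitor reviews all reported adverse events, and the DSMB sees compiled safety data. Repeats are recorded but not summarized.
- *That the plan makes an invalid comparison between phases.* The tabulation is descriptive, and no formal safety test is proposed. Phase 3 results are to be submitted separately from Phase 2.
- *That a rise in Pod events from Phase 1 to Phase 2 would be an artefact of exposure.* In Phase 1 children stay on their own MDI or pump therapy, and the study system is dispensed at Visit 4. For a child not already using a Pod (apart from the optional saline trial), a rise in Pod-specific events would be real. The constant-rate illustration fits background events and the step from Phase 2 to Phase 3 better than it fits Pod events between Phases 1 and 2.

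It is also fair to say that the rates are assumed, that the reporting thresholds are narrow, and that a Phase 1 rate will be imprecise. These limit the size of the point and the use of Phase 1 as a comparator. They do not make the percentage a better summary than the rate.

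**Conclusion.** The point holds as a descriptive reporting weakness. For adverse events other than severe hypoglycemia and DKA, and by reference for device deficiencies, the plan specifies only once-per-child counts and percentages by phase, without exposure. Percentages can differ between phases through exposure alone; the documents do not show that they must. At an assumed 0.02 to 0.10 events per person-month, the table leaves out about 3-14% of events in Phase 2, the phase intended for marketing clearance, and 11-41% over 356 days. These figures rest on a constant Poisson rate and full follow-up. Lower rates shrink them and clustering enlarges them. No endpoint, significance level or sample size changes. The case for acting is that the remedy is cheap and the affected events are the device harms most able to recur.

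**What to change.** In SAP 5.4, with matching wording in Protocol 13.6.1, keep the subject counts and percentages. At least for prolonged hyperglycemia/ketotic events and Pod- or CGM-site events, add by phase:
- the number of events, including repeats;
- the number of children who entered the phase;
- the person-months of exposure;
- events per person-month, with a confidence interval that allows for clustering within child.

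Also state that any descriptive reading across phases uses the rate, that Phase 1 exposure is sparse (at most about 37 person-months for 80 children at 14 days), and that Pod-specific events are not expected in Phase 1 in children not using a Pod. The two documents should also agree on when Phase 3 ends, since that sets its person-time.

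The cost is SAP and protocol wording and a few columns in tables already planned. No new data collection appears necessary, since adverse events and phase visits are already recorded. The downside is slightly longer tables.
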